**22.12.20203**

**Valdivia, Chile**

## Problem Statement and State of the Art

As the global population ages, disease patterns shift, and cardiovascular risk factors (CRFs) increase (1). The onset of CRFs at an earlier age has been reported, and according to the 2017 Chilean National Health Survey, there is a high prevalence of physical inactivity (86.7%), overweight (39.8%), obesity (31.2%), morbid obesity (3.2%), suspected hypertension (27.6%), and type 2 diabetes mellitus (12.3%) (2).

Physical inactivity, defined as not meeting international physical activity recommendations ( $\geq 150$  minutes of moderate to vigorous physical activity per week, or achieving an energy expenditure  $\geq 600$  MET/min/week) (3), has been shown to be a predominant factor for the earlier onset of CRFs (4). Inactivity leads to early onset of insulin resistance at the muscular level and the shift of muscle fibers from oxidative to glycolytic, decreasing the use of lipids as an energy substrate. These unoxidized lipids accumulate in central and peripheral adipose tissue and organs as ectopic fat, which increases sympathetic activity and inflammatory response; processes associated with alterations in metabolic flexibility (5, 6) and high risk of hypertension, type 2 diabetes mellitus, dyslipidemia, obesity (7, 8), and non-oncologic chronic pain (9, 10, 11).

Specifically, metabolic flexibility is defined as the ability to efficiently adapt our metabolism through the detection, trafficking, storage, and utilization of energy substrates, depending on availability and requirements (12). It has been described that metabolic disorders, as mentioned earlier, limit this capacity for physiological adaptability (13); this metabolically 'inflexible' state is characterized by inefficient glucose transport, reduced fatty acid turnover, and diminished oxidative capacity, favoring the accumulation of ectopic lipids and the early onset of metabolic syndrome (14).

Regarding non-oncologic chronic pain, it is recognized as a disease in its own right (15), with a prevalence of 32.1% in the Chilean population (16), becoming a public health issue, negatively impacting quality of life, user function, representing a high socioeconomic burden (17, 18). Some metabolic disorders (e.g., diabetes mellitus, hypertension, and obesity) have been linked to the development and progression of non-oncologic chronic pain (9, 10, 11). Furthermore, individuals with non-oncologic chronic pain and cardiovascular diseases experience greater pain severity and disability than those with chronic pain alone (19). People with chronic pain often experience functional limitation, which is associated with low levels of physical activity, sedentary behavior, increasing the risk of developing cardiovascular diseases (19).

In this context, individuals with CRFs may enter the Cardiovascular Health Program (PSCV), which aims to reduce the incidence of cardiovascular events through the control and compensation of CRFs in primary care through the following actions:

- Reducing the cardiovascular risk of controlled individuals.
- Promoting healthy lifestyles.
- Achieving control of risk factors.
  - Achieving optimal blood pressure levels.
  - Improving metabolic control in people with diabetes.
  - Improving cholesterol levels in individuals with dyslipidemia.

Complementing the actions of the PSCV, physical exercise becomes a cornerstone for the control of these CRFs (20), improvement in metabolic flexibility (21), and reduction of non-oncologic chronic pain associated with CRFs (22, 23). Moderate-intensity aerobic exercise for 30 to 60 minutes every day of the week has been described as the most used alternative for controlling these risk factors (24); however, achieving this volume of exercise is very difficult in a clinical setting. Since lifestyle change is not easy for the population, adherence to some aerobic exercise programs decreases up to 50% in the first 3 months (25). Factors responsible for this low adherence include session duration, the presence of disease or post-exercise pain, and lack of time reported by users (26).

Thus, time-effective exercise alternatives ( $\leq 10$  minutes of effective work) could address this reported lack of time by users and achieve control of CRFs. Among the time-effective exercise modalities for controlling CRFs, high-intensity interval training (HIIT) (27) has been reported, consisting of repeated short periods of high-intensity exercise followed by passive or active low-intensity breaks (28), and muscle resistance exercises with elastic materials (ERE) which is a method that uses elastic devices as resistance, which are low-cost, portable, and can be used almost anywhere. Elastic devices allow for modulating training intensity by changing the resistance provided by the bands (29).

Positive results have been reported from HIIT and ERE exercise programs for reducing blood pressure (27, 29), improving glycemic control (30, 31), body composition (27, 32), metabolic flexibility (21), physical function (32, 33), and reducing non-oncologic chronic pain (34, 35) in users of this cohort.

An important aspect that reveals the true effect of an exercise program is the adaptations to workload understood as the physiological changes or adjustments resulting from a physical training program that promotes optimal functioning of the organism (36). Adaptations are determined by events that result in the activation and/or repression of specific signaling pathways that regulate exercise-induced gene expression and protein synthesis/degradation (37). The functional consequences of

these adaptations are determined by the training volume, intensity, and frequency, and the half-life of the protein (38). Moreover, many characteristics of training adaptation are specific to the type of stimulus, such as the mode of exercise (38). HIIT-type exercise induces a variety of metabolic and morphological changes, including mitochondrial biogenesis, fiber type transformation from fast to slow, and substrate metabolism (39). In contrast, resistance exercise (ERE) stimulates the synthesis of contractile proteins responsible for muscle hypertrophy and increases the production of maximum contractile force (37, 38).

Generally, the results of exercise programs show the final changes after an intervention, leaving aside the capacity for adaptation to workload during the intervention. The processes of adaptation to exercise are studied mainly in athletes; however, little is known about the adaptability capacity, in special populations, regarding CRFs, metabolic flexibility, physical function, and non-oncologic chronic pain, specifically in users belonging to the Cardiovascular Health Program of the External CESFAM of Valdivia, subjected to two types of exercise.

Despite knowing the link between non-oncologic chronic pain and the presence of cardiovascular diseases, the individual relationship between different cardiovascular risk factors and pain intensity is still uncertain.

Thus, implementing a physical exercise program associated with the PSCV will improve the possibility of controlling CRFs, improving metabolic flexibility, reducing non-oncologic chronic pain, and promoting lifestyle change difficult to achieve in users of this cohort. On the other hand, the External CESFAM will be recognized as a pioneering establishment in the implementation of non-pharmacological alternatives (personalized and expert-guided physical exercise) to improve the health and quality of life of PSCV users, which will not generate extra costs to the establishment for its application.

## **Objectives**

### **General**

- Objective 1: Evaluate the effects of a 12-week HIIT and ERE program on the workload adaptation capacity in cardiometabolic risk factors, physical function, and non-oncologic chronic pain in users of the Cardiovascular Health Program at the External CESFAM of Valdivia.
- Objective 2: Determine the relationship between cardiovascular risk factors and non-oncologic chronic pain in users of the Cardiovascular Health Program at the External CESFAM of Valdivia.

## **Specific**

- Objective 1.1: Analyze the effects of a 12-week HIIT and ERE program on the workload adaptation capacity in cardiometabolic risk factors, physical function, and non-oncologic chronic pain in users of the Cardiovascular Health Program at the External CESFAM of Valdivia.
- Objective 1.2: Compare the effects of a 12-week HIIT and ERE program on the workload adaptation capacity in cardiometabolic risk factors, physical function, and non-oncologic chronic pain in users of the Cardiovascular Health Program at the External CESFAM of Valdivia.
- Objective 2.1: Determine the relationship between the number of cardiovascular risk factors and the presence of non-oncologic chronic pain in users of the PSCV at the External CESFAM of Valdivia.
- Objective 2.2: Determine the relationship between the number of cardiovascular risk factors and the intensity of non-oncologic chronic pain in users of the PSCV at the External CESFAM of Valdivia.
- Objective 2.3: Associate the presence of non-oncologic chronic pain with other chronic diseases.

## **Methodology**

The project formulation, planning, and management, the application of assessments, and exercise protocols will be carried out by a team of kinesiologists experienced in physical exercise and control of CRFs, supported by the Kinesiology school of the Universidad San Sebastián, Valdivia campus. This project will complement the actions of the PSCV of the External CESFAM of Valdivia. All evaluations and interventions will contribute to the Monthly Statistical Register (REM) of the PSCV, specifically, in the REM A27 (health education) section C (group physical activity for the cardiovascular health program) and, depending on the case, in REM A04 section B: Consultation with non-medical professionals. Both records will be collected by the providers (USS) and sent to the PSCV reference of the External CESFAM, ideally on the last day of the month, to contribute to REM. The results obtained during the intervention could be published in press articles, conferences, and renowned scientific journals to disseminate the good practices carried out by the CESFAM. The population will correspond to adult users of the PSCV enrolled in the External CESFAM of Valdivia with CRFs, the sample will be obtained through a public call inviting participation in HIIT or ERE exercise 3 sessions weekly for 12 weeks at the San Sebastián University Physical Fitness and Exercise Facility. The Cardiovascular Health Program team (Medical Director [name]) will identify eligible users

for the study within the records (clinical file and health controls) of the program, then the PSCV team will extend the invitation to users to participate in the project.

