### **Inclusion and Exclusion Criteria**

Inclusion: a) Being physically inactive (not performing 300 or 150 min of moderate or vigorous intensity physical activity respectively per week measured with the IPAQ questionnaire); b) BMI between 25 and 39.9 kg/m^2; c) Belonging to the cardiovascular health program of the External CESFAM of Valdivia d) Presenting with or without non-oncologic chronic pain.

Exclusion: a) Bone disease; b) Ischemic disease or arrhythmia and c) Chronic respiratory disease d) Uncontrolled chronic diseases f) People unable to understand instructions, g) People who do not speak Spanish h) History of previous oncological disease or under study for suspected neoplastic disease in any part of the body i) Low adherence to training (< 70% or non-attendance at 4 continuous sessions).

Included users will be divided into 3 groups: HIIT, ERE, and Control. All subjects will be evaluated at four times: pre-intervention (week 0 – time 1), week 4 (time 2), week 8 (time 3), and post-intervention (week 12 – time 4). Only the evaluation of metabolic flexibility and direct oxygen consumption will be carried out pre (week 0) and post-intervention (week 12).

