#### **Six-Minute Walk Test**

The Six-Minute Walk Test (6MWT) is a simple and effective submaximal exercise test used to assess aerobic functional capacity, especially in patients with cardiopulmonary and respiratory diseases. The main objective of this test is to measure the distance an individual can walk over a span of six minutes on a flat, hard surface. This test is widely used because it is easy to perform, does not require sophisticated equipment, and reflects activities of daily living.

The general protocol of the 6MWT includes the following steps:

1. Preparation: Before the test, the procedure is explained to the patient, and consent is obtained. Baseline measurements such as heart rate, blood pressure, and oxygen saturation should be recorded.
2. Instructions: The patient is instructed to walk at their own pace but to try to cover the greatest distance possible in six minutes. They are allowed to slow down or stop if necessary.
3. Conducting the Test: During the test, the patient walks along a marked hallway, turning around at the end of each stretch. The evaluator follows the patient to assist if necessary but without encouragement to not influence performance.
4. Post-test: Immediately after the test, heart rate, blood pressure, and oxygen saturation are re-measured. The total distance covered is also recorded.
5. Results Analysis: The distance walked is compared to reference values based on the patient's age, gender, and other variables to assess their functional capacity.

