### Grip Dynamometry

Grip strength will be assessed using the CAMRY Model EH101 dynamometer (46) following the Southampton protocol. The procedure begins with the subject seated with forearms resting on the chair, the wrist just over the end of the chair arm, in a neutral position, with the thumb up and feet flat on the floor, they are asked to squeeze the dynamometer as hard as they can for as long as they can. Three attempts will be made with each hand and the best attempt of the 6 total will be recorded (47).

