## **Pressure Pain Threshold**

The Pressure Pain Threshold (PPT) is defined as the minimum amount of pressure that elicits the first sensation of pain, and will be measured using a pressure algometer (53).

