## **Statistical Analysis**

The sample size will be calculated as follows: (1) ANOVA for repeated measures with intra-inter-group interaction, (2) three groups, (3) type I error: 5%, (4) type II error: 20%, (5) statistical test power: 80%, and (6) effect size (ES): 0.10 according to Cohen's classification (1988). Using these parameters, the total sample size recommended by G\*Power software (Version 3.1.9.2) was 174 (58 per group). Assuming a 10% dropout, the total was calculated at 192, with 64 participants randomly assigned to each group. The concealment of allocation will be conducted by a researcher not involved in the clinical procedures of the intervention using the

method of opaque, sealed, and consecutively numbered envelopes. The random sequence and allocation concealment allow for the control of selection bias.

For enhanced bias control, the data analysis will be performed by a researcher blinded to the intervention groups. Dependent variables will be described in terms of mean and standard deviation. Assumptions of normality and homoscedasticity for all data will be verified using the Shapiro-Wilk test and the Levene's test, respectively. To address General Objective 1, the Student's t-test will be used to detect baseline differences between groups, and a repeated measures ANOVA (group x time) to determine differences in all dependent variables between training prior, and at 4, 8, and 12 weeks afterwards. The Bonferroni post hoc test will be used to test differences between groups. Additionally, the Cohen's d test will be applied to determine the effect size. To address the General Objective, the Pearson correlation test will be used to determine the relationship between MHR and the presence and intensity of non-oncological chronic pain. The level for statistical significance was set at  $p < 0.05$ . Statistical analyses will be performed using SPSS software version 21 (SPSS™ Inc., Chicago, IL, USA).

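### One team both trains and tests, and only the data analyst is blinded, so examiner expectation can enter the pressure pain threshold, grip and walk-test comparisons with control

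*Combined protocol and SAP*

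**What the plan says.** The Methodology section assigns training and testing to the same group of staff: "the application of assessments, and exercise protocols will be carried out by a team of kinesiologists experienced in physical exercise and control of CRFs". It does not say how the two jobs are divided within the team.

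The Statistical Analysis section contains two bias controls.
- Blinding: "the data analysis will be performed by a researcher blinded to the intervention groups".
- Allocation: "The concealment of allocation will be conducted by a researcher not involved in the clinical procedures of the intervention". The stated purpose is limited: "The random sequence and allocation concealment allow for the control of selection bias".

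No section describes a blinded outcome assessor or a separation of trainers from testers.

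Three tests rest on participant effort or report and on how the examiner conducts them.
- Six-Minute Walk Test: "The evaluator follows the patient to assist if necessary but without encouragement to not influence performance".
- Grip Dynamometry: "they are asked to squeeze the dynamometer as hard as they can for as long as they can". A named protocol fixes the position, and the best of six attempts is recorded.
- Pressure Pain Threshold: defined as "the minimum amount of pressure that elicits the first sensation of pain, and will be measured using a pressure algometer". No site, rate of pressure, number of repeats or examiner is given.

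There are three arms, one of them an untrained control (Inclusion and Exclusion Criteria; Control Group), and these tests are repeated at weeks 0, 4, 8 and 12.

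**The concern.** Team members who run three sessions a week for 12 weeks will know which participants train, and controls do not attend those sessions. If the same people then run the tests, their knowledge of the arm divides exactly along the exercise-versus-control line. A tester who expects improvement may urge a little more effort at the dynamometer or apply the algometer a little differently. The Expected Results section states the anticipated direction in advance.

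Physical function and chronic pain are named in General Objective 1 and in Objectives 1.1 and 1.2, so the exposed tests serve the main objective. A systematic difference in how the arms are tested adds to the apparent exercise effect. Blinding the analyst does not help, because the difference is already in the recorded values. Allocation concealment does not help either, because it acts before the tests are done.

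**Working it through.** **Step 1. Which safeguard covers which route.**

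| Route of bias | Safeguard in the plan | Covers the examiner at weeks 4, 8 and 12? |
|---|---|---|
| Who enters which arm | Random sequence, sealed envelopes, independent researcher | No; tied to selection bias |
| Choices made in the analysis | Blinded analyst | No; acts after recording |
| Examiner, walk test | Rule against encouragement | Partly; the arm is not hidden |
| Examiner, grip | Named protocol, fixed position, best of six | Partly; the arm is not hidden |
| Examiner, pressure pain threshold | None stated | No |

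Fasting glucose, cholesterol and triglycerides come from routine programme tests (Metabolic Parameters) and are not exposed to this route.

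**Step 2. The plan's sample size.** This is not in dispute; it is reproduced to fix the number per arm. Inputs from Statistical Analysis: effect size 0.10 (read as Cohen's f), three groups, alpha 5%, power 80%. Four times come from Inclusion and Exclusion Criteria. A within-person correlation of 0.5 and sphericity are assumed, because neither is stated.
- Noncentrality: λ = f² × N × m / (1 − ρ) = 0.01 × 174 × 4 / 0.5 = 13.92.
- Degrees of freedom: (3 − 1)(4 − 1) = 6 and (174 − 3)(4 − 1) = 513.
- Power = 0.804, so 174 (58 per group) is reproduced.

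**Step 3. Illustration for one pairwise comparison.** Assume no true effect and a shift of b SD, from testing alone, in one exercise arm against control. With n = 58 per arm, the noncentrality of the two-sample t-test is b × √(n/2) = b × √29 = 5.385 × b, on 114 degrees of freedom. The two-sided critical values are 1.981 at alpha 0.05 and 2.430 at 0.05/3 = 0.0167.

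| Assumed shift (SD) | Noncentrality | Chance of p < 0.05, unadjusted | Chance of significance, Bonferroni for three pairs |
|---|---|---|---|
| 0 | 0 | 5.0% | 1.7% |
| 0.1 | 0.539 | 8.3% | 3.3% |
| 0.2 | 1.077 | 18.7% | 9.2% |
| 0.3 | 1.616 | 36.0% | 21.2% |

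**Step 4. The planned group × time test.** Suppose the same shift affects both trained arms at weeks 4, 8 and 12 and is absent at baseline. The squared interaction terms over the 3 × 4 cell means sum to 0.5 × b². Then λ = 58 × 0.5 × b² / (1 − ρ) = 29 × b² / (1 − ρ), with 6 and 513 degrees of freedom.
- ρ = 0.5: the test rejects in about 7%, 16% and 35% of trials for b = 0.1, 0.2 and 0.3, against a nominal 5%.
- ρ = 0.7: about 9%, 26% and 57%.

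**Step 5. HIIT against ERE.** If testing shifts both trained arms by the same b, the contrast between them carries b − b = 0. Only a difference in shift between the two programmes would remain.

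**The case against.** The strongest reply is that the text leaves the division of work unstated; it does not assign a participant's trainer to be that participant's tester. That stands. A reader might infer that the same person trains and tests each participant, but the plan speaks of a team, and a split of roles is not excluded. A reader might also infer that expectation bias does enter the results. The documents show an open route, not that anyone will take it or how far.

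The plan also has real, if partial, controls. Barring encouragement in the walk test restrains the examiner directly, and grip follows a named protocol. Distance and grip force are measured quantities, so urging more effort is a more plausible route than generous scoring. The three tests are therefore not equally exposed. The pressure pain threshold, for which no procedure is given, is the weakest.

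The percentages rest on assumed shifts. The unadjusted t-test is not the planned analysis, which is a repeated-measures ANOVA with Bonferroni post hoc tests. The Bonferroni and group × time figures meet the second criticism; nothing in the documents can meet the first. A reader might take these figures as predicted false-positive rates, and they are not.

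Finally, team size is not stated, so full separation may not be feasible. Even full separation would leave participants' own expectation in place, because they know whether they exercise.

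What survives is that no statement in the plan hides the arm from the person running these tests or keeps trainers from testing those they train.

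**Conclusion.** The point holds as a weakness of design. As written, the plan leaves an uncontrolled route by which examiner expectation can affect the pressure pain threshold, and to a lesser degree grip and the walk test. It bears mainly on HIIT-versus-control and ERE-versus-control. A bias shared by both trained arms would largely cancel between HIIT and ERE, and the laboratory values are outside its reach.

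The size is unknown. The illustration shows only that, at 58 per arm, shifts of 0.2 to 0.3 SD would be enough to raise the error rate several-fold: from 1.7% to between 9% and 21% per pair under Bonferroni. It assumes no true effect, a constant shift in SD units and, for the group × time test, a within-person correlation that the documents do not give. It explains why the route is worth closing and does not estimate what will happen. The calculation does not call the sample size of 174 into question.

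**What to change.** Add to the Methodology section, before the week 4 tests begin:
- Walk, grip and pressure pain threshold tests at weeks 4, 8 and 12 are rostered to members of the existing team who do not train those participants and are not told their arm.
- The same scripted instructions are used in all arms. For the pain threshold, the script also sets out how the algometer is applied, since the plan gives no procedure.
- Participants are asked not to reveal their arm, and each occasion on which a tester learns it is logged.

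If the team is too small for full separation, the minimum is that nobody tests a participant they train, and the report states that assessors were not fully blinded. If roles are already separated in practice, the protocol should say so.

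The cost is a staff roster, a script and a few sentences of protocol text. Scheduling becomes less flexible and blinding will sometimes be broken. The change reduces the examiner's share of the bias and leaves that of participants, who cannot be masked to exercise. It has to be made before testing, because no analysis can recover it afterwards.
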